- for treatment of irritability associated with autistic disorder in children and adolescents (ages 6 to 17 years).

In the European Union (EU), aripiprazole is also approved for the treatment of moderate to severe manic episodes in bipolar I disorder and for the prevention of new manic episodes in those patients who experienced predominantly manic episodes and whose manic episodes responded to aripiprazole treatment, as well as for the treatment of schizophrenia in adults and adolescents ([Appendix 13](#)). The aripiprazole immediate-release IM injection formulation is approved for the treatment of agitation associated with schizophrenia or bipolar mania in the US and EU. In addition, an oral solution formulation and orally disintegrating (dispersible) tablets have been approved and marketed in the US and EU.

The favorable side effect profile of oral aripiprazole, including its low incidence of EPS, low risk of prolactin elevation, decreased adrenergic and anticholinergic side effects, and minimal weight gain, makes it an excellent candidate for a long-acting depot formulation. Aripiprazole IM depot formulation is currently being developed for maintenance treatment of schizophrenia and bipolar I disorder, and was approved for the treatment of schizophrenia in the US in February 2013. Its efficacy was demonstrated in a pivotal phase 3 registrational trial (Study 31-07-246) designed to evaluate the efficacy, safety, and tolerability of the long-acting IM depot formulation of aripiprazole administered to adult subjects with a diagnosis of schizophrenia as defined by the Diagnostic and Statistical Manual of Mental Disorders, Fourth Edition, Text Revision (DSM-IV-TR). A marketing application was submitted in September 2011 to the Food and Drug Administration (FDA) for use of the aripiprazole IM depot formulation as maintenance treatment in patients with schizophrenia, which was approved in February 2013 ([Appendix 13](#)). A marketing application was submitted in December 2012 to the European Medicines Agency.

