Aripiprazole IM Depot treatment in this open-label rollover study will continue until there are clinical and/or administrative reasons for discontinuation of the subject's study treatment or until the study end date of 31 Dec 2018 is reached, whichever occurs first. Clinical reasons for discontinuing study treatment include, but are not limited to: the subject voluntarily withdraws consent; the subject becomes lost to follow-up; if a subject misses 2 consecutive injections at any time in the study or 3 injections in any 52-week time period; or the investigator determines that the subject is no longer receiving benefit from aripiprazole IM Depot. Administrative reasons for discontinuing study treatment include, but are not limited to: aripiprazole IM Depot is commercially available in any dosage (including a generic formulation) in the country where the study is being conducted, the commercial availability of aripiprazole IM Depot is terminated by the sponsor, or until the study end date of 31 Dec 2018 is reached, whichever occurs first.

If the sponsor terminates the study prior to 31 Dec 2018 for any reason other than commercial availability, investigators in some countries where the sponsor has limited or delayed commercialization plans, or where no commercialization activity is anticipated, may be eligible to participate in a managed access program until aripiprazole IM Depot is commercially available in their country or until 31 Dec 2018. Availability and requirements of such a program varies by jurisdiction, and would only be an option for subjects who were receiving aripiprazole IM Depot in the current study, and who in the physician's opinion, may benefit from continued treatment with aripiprazole. To gain access to aripiprazole IM Depot for eligible subjects via a managed access program, each physician will be responsible for gaining appropriate local regulatory approvals, which will be granted by authorities on a case-by-case basis. The sponsor makes no guarantee that such a program is available or approvable in all of the jurisdictions where the study is conducted.

Once aripiprazole IM Depot becomes commercially available in the country where the subject is participating in the study (including generic formulation[s]) or the commercial availability of aripiprazole IM Depot is terminated by the sponsor, study treatment will be discontinued within approximately 6 weeks of the subject's previous injection for clinical transition purposes.

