3.6.1.2 Injection and Assessments Performed Every Month

Monthly assessments (study months are every 4 weeks which is defined as 28 [-2/+10] days) include a C-SSRS assessment and recording of AEs experienced since the last visit and concomitant medications, followed by the aripiprazole IM Depot injection. The monthly injections and assessments should be performed on Study Months 1 through 104.

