3.7 Stopping Rules, Withdrawal Criteria, and Procedures

3.7.1 Entire Trial or Treatment Arm(s)

The sponsor should be notified promptly if the trial is terminated at your site. If the sponsor decides to terminate or suspend the trial for safety or unanticipated other reasons or if aripiprazole IM Depot becomes commercially available in the country of the study site, the sponsor will promptly notify investigators, IRBs/IECs, and regulatory authorities as required by the applicable regulatory requirements.

The sponsor will terminate the study in countries where aripiprazole IM Depot becomes commercially available (including generic formulation[s]), the commercial availability of aripiprazole IM Depot is terminated by the sponsor, or if the study end date of 31 Dec 2018 is reached.

If the sponsor terminates the study prior to 31 Dec 2018 for any reason other than commercial availability, investigators in some countries where the sponsor has limited or delayed commercialization plans, or where no commercialization activity is anticipated, may be eligible to participate in a managed access program until aripiprazole IM Depot is commercially available in their country or until 31 Dec 2018. Availability and requirements of such a program varies by jurisdiction, and would only be an option for subjects who were receiving aripiprazole IM Depot in the current study, and who in the physician's opinion, may benefit from continued treatment with aripiprazole. To gain access to aripiprazole IM Depot for eligible subjects via a managed access program, each physician will be responsible for gaining appropriate local regulatory approvals, which will be granted by authorities on a case-by-case basis. The sponsor makes no guarantee that such a program is available or approvable in all of the jurisdictions where the study is conducted.

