7.3 Primary Outcome Measures

In this safety and tolerability study, the primary measures are (1) frequency and severity of adverse events, (2) frequency and severity of serious adverse events (including adverse events related to laboratory abnormalities), and (3) rates of discontinuation from study due to adverse events.

Safety and tolerability data will be summarized as follows: Incidence of adverse events and serious adverse events (with severity grades) will be tabulated by Medical Dictionary for Regulatory Activities (MedDRA) terms; similarly, incidence of discontinuations due to AE will be tabulated by MedDRA terms.

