## **5.5 Safety Analyses**

### **5.5.1 Adverse Events**

All adverse events (AEs) are coded by system organ class and Medical Dictionary for Regulatory Activities (MedDRA) preferred term (Version 21.0 or later). A treatment-emergent AE (TEAE) is defined as an AE which starts after start of trial medication (Aripiprazole IM Depot), or an AE continues from baseline and becomes serious, worsening, trial drug-related or results in death, discontinuation, interruption or reduction of trial medication during this trial. All ongoing AEs and clinically significant AEs from

Trial 248 are recorded as Medical History for this trial. If the AE increases severity or frequency during this trial period, a new AE are recorded. The incidences of the following treatment-emergent adverse events (TEAEs) will be summarized for the safety sample:

- TEAEs by severity
- Potentially drug-related TEAEs
- TEAEs with an outcome of death
- Serious TEAEs
- Discontinuations due to TEAEs

Listing and incidences of AEs described above are tabulated for the safety sample.

Deaths, SAEs, and AEs leading to discontinuation from trial or trial treatment are listed for the enrolled sample. In addition, incidences of TEAEs will be provided for the following subgroup analyses: region (US, non-US), sex (male, female), race (Caucasian, Black or African American, American Indian or Alaska Native, Asian, other), age (< 45 years old,  $\geq 45$  years old), ethnicity (Hispanic or Latino, not Hispanic or Latino), and BMI at baseline ( $\leq 28$  kg/m^2,  $> 28$  kg/m^2).

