## Appendix 4 Table of Contents for Tables and Listings

### Clinical Summary Tables

CT-1.1	SUBJECT DISPOSITION
CT-1.2	SUBJECT DISPOSITION BY REGION, COUNTRY AND CENTER
CT-1.3	SUBJECT DURATION BY MONTH
CT-1.4	ENROLLMENT BY COUNTRY
CT-1.5	ENROLLMENT BY COUNTRY BY AGE GROUP
CT-2	REASONS FOR DISCONTINUATION
CT-3	DEMOGRAPHIC CHARACTERISTICS BY SEX
CT-4.1	CONCOMITANT MEDICATIONS TAKEN PRIOR TO STUDY PERIOD
CT-4.2	CONCOMITANT MEDICATIONS TAKEN DURING STUDY PERIOD
CT-4.3	CONCOMITANT MEDICATIONS TAKEN POST STUDY PERIOD
CT-4.4	CONCOMITANT BENZODIAZEPINES AND ANTICHOLINERGICS USE
CT-5	CGI SEVERITY SCORE - MEAN CHANGE FROM BASELINE BY MONTH - OC
CT-6.1.1	SIMPSON-ANGUS SCALE TOTAL SCORE - MEAN CHANGE FROM BASELINE BY MONTH - OC
CT-6.1.2	BARNES AKATHISIA GLOBAL SCORE - MEAN CHANGE FROM BASELINE BY MONTH - OC
CT-6.1.3	AIMS MOVEMENT RATING SCORE - MEAN CHANGE FROM BASELINE BY MONTH - OC
CT-6.2.1	COLUMBIA-SUICIDE SEVERITY RATING SCALE (C-SSRS) - INCIDENCE OF SUICIDALITY
CT-6.2.2	COLUMBIA-SUICIDE SEVERITY RATING SCALE (C-SSRS) - INCIDENCE OF SUICIDALITY BY TYPE
CT-6.2.3	COLUMBIA-SUICIDE SEVERITY RATING SCALE (C-SSRS) - MEAN CHANGE FROM BASELINE IN SUICIDAL IDEATION INTENSITY TOTAL SCORE
CT-7.1	EXTENT OF EXPOSURE TO STUDY MEDICATION - ARIPIPRAZOLE IM DEPOT
CT-7.2	DESCRIPTIVE STATISTICS FOR STUDY DAYS OF ARIPIPRAZOLE IM DEPOT INJECTIONS
CT-7.3	EXTENT OF EXPOSURE TO STUDY MEDICATION BY INJECTION DOSE - ARIPIPRAZOLE IM DEPOT
CT-8.1	INCIDENCE OF ADVERSE EVENTS (ALL CAUSALITIES)
CT-8.2.1	INCIDENCE OF TREATMENT-EMERGENT ADVERSE EVENTS BY SYSTEM ORGAN CLASS
CT-8.2.2	INCIDENCE OF TREATMENT-EMERGENT ADVERSE EVENTS BY SYSTEM ORGAN CLASS AND MEDDRA PREFERRED TERM
CT-8.2.3	INCIDENCE OF TREATMENT-EMERGENT ADVERSE EVENTS BY SYSTEM ORGAN CLASS, MEDDRA PREFERRED TERM AND SEVERITY
CT-8.2.4.1	INCIDENCE OF TREATMENT-EMERGENT ADVERSE EVENTS GREATER THAN 5% BY SYSTEM ORGAN CLASS AND MEDDRA PREFERRED TERM
CT-8.2.4.2	INCIDENCE OF TREATMENT-EMERGENT ADVERSE EVENTS BY MEDDRA PREFERRED TERM IN DESCENDING ORDER OF INCIDENCE RATE FOR TOTAL
CT-8.2.4.3	INCIDENCE OF NON-SERIOUS TREATMENT-EMERGENT ADVERSE EVENTS OCCURRING IN AT LEAST 5% OF THE SUBJECTS BY SYSTEM ORGAN CLASS AND MEDDRA PREFERRED TERM
CT-8.2.4.4	OCCURRENCE (NUMBER OF EVENTS) OF NON-SERIOUS TREATMENT-EMERGENT ADVERSE EVENTS BY SYSTEM ORGAN CLASS AND MEDDRA PREFERRED TERM
CT-8.2.5	INCIDENCE OF TREATMENT-EMERGENT EPS ADVERSE EVENTS

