CT-13.2.4	LABORATORY TEST RESULTS FOR OTHER LABORATORY TESTS - MEAN CHANGE FROM BASELINE
CT-13.2.5.1	INCIDENCE OF PROLACTIN LEVEL ABOVE UPPER LIMIT OF NORMAL RANGE BY SEX
CT-13.2.5.2	LABORATORY TEST RESULTS FOR PROLACTIN - MEAN CHANGE FROM BASELINE BY SEX
CT-14.1	INCIDENCE OF VITAL SIGNS OF POTENTIAL CLINICAL RELEVANCE
CT-14.2	INCIDENCE OF POTENTIALLY CLINICALLY RELEVANT WEIGHT GAIN OR LOSS
CT-14.3	MEAN CHANGE FROM BASELINE IN VITAL SIGNS PARAMETERS
CT-15.1	INCIDENCE OF ECG MEASUREMENTS OF POTENTIAL CLINICAL RELEVANCE
CT-15.2	ECG PARAMETERS - MEAN CHANGE FROM BASELINE
CT-15.3	INCIDENCE OF CATEGORICAL INCREASES IN ECG - QTC
CT-16.1	VISUAL ANALOG SCALE SCORE FOR SUBJECT-REPORTED RATING OF PAIN AT MOST RECENT INJECTION SITE - MEAN SCORE
CT-16.2.1	PROPORTION OF SUBJECTS AT EACH LEVEL OF INVESTIGATOR'S ASSESSMENT OF MOST RECENT INJECTION SITE - PAIN
CT-16.2.2	PROPORTION OF SUBJECTS AT EACH LEVEL OF INVESTIGATOR'S ASSESSMENT OF MOST RECENT INJECTION SITE - SWELLING
CT-16.2.3	PROPORTION OF SUBJECTS AT EACH LEVEL OF INVESTIGATOR'S ASSESSMENT OF MOST RECENT INJECTION SITE - REDNESS
CT-16.2.4	PROPORTION OF SUBJECTS AT EACH LEVEL OF INVESTIGATOR'S ASSESSMENT OF MOST RECENT INJECTION SITE - INDURATION
CT-17.1	INCIDENCE OF TREATMENT-EMERGENT ADVERSE EVENTS BY SYSTEM ORGAN CLASS AND MEDDRA PREFERRED TERM BY REGION (US VS NON-US)
CT-17.2	INCIDENCE OF TREATMENT-EMERGENT ADVERSE EVENTS BY SYSTEM ORGAN CLASS AND MEDDRA PREFERRED TERM BY SEX
CT-17.3	INCIDENCE OF TREATMENT-EMERGENT ADVERSE EVENTS BY SYSTEM ORGAN CLASS AND MEDDRA PREFERRED TERM BY RACE
CT-17.4	INCIDENCE OF TREATMENT-EMERGENT ADVERSE EVENTS BY SYSTEM ORGAN CLASS AND MEDDRA PREFERRED TERM BY AGE GROUP
CT-17.5	INCIDENCE OF TREATMENT-EMERGENT ADVERSE EVENTS BY SYSTEM ORGAN CLASS AND MEDDRA PREFERRED TERM BY ETHNICITY
CT-17.6	INCIDENCE OF TREATMENT-EMERGENT ADVERSE EVENTS BY SYSTEM ORGAN CLASS AND MEDDRA PREFERRED TERM BY BMI
CT-18.1	VISUAL ANALOG SCALE SCORE FOR SUBJECT-REPORTED RATING OF PAIN AT MOST RECENT INJECTION SITE - MEAN SCORE BY INJECTION

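### Adverse event summaries have no person-time denominator, although follow-up can run from weeks to about 8 years and depends partly on country launch

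*SAP*

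**What the plan says.** **Adverse event analysis.** Protocol 7.3 makes adverse events, serious adverse events and discontinuations due to adverse events the primary outcome measures: "Incidence of adverse events and serious adverse events (with severity grades) will be tabulated". SAP 5.5.1 carries this through as incidences of treatment-emergent adverse events (TEAEs) and adds subgroups: "incidences of TEAEs will be provided for the following subgroup analyses: region (US, non-US"), with sex, race, age, ethnicity and BMI. The regional table is CT-17.1 in Appendix 4: "INCIDENCE OF TREATMENT-EMERGENT ADVERSE EVENTS BY SYSTEM ORGAN CLASS AND MEDDRA PREFERRED TERM BY REGION (US VS NON-US"). Three tables give event counts rather than subjects: CT-8.2.4.4 ("OCCURRENCE (NUMBER OF EVENTS) OF NON-SERIOUS TREATMENT-EMERGENT ADVERSE EVENTS"), CT-8.5.4 and CT-8.5.5. SAP 5.1.1 also splits the data by enrolment source into Study 248.

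**Follow-up.** Protocol 3.6.1.2 sets the longest schedule: "The monthly injections and assessments should be performed on Study Months 1 through 104". Treatment stops earlier for clinical reasons, on 31 Dec 2018, or on launch. Protocol 3.7.1 states: "The sponsor will terminate the study in countries where aripiprazole IM Depot becomes commercially available". Protocol 3.1 adds that after launch "study treatment will be discontinued within approximately 6 weeks of the" subject's previous injection. Protocol section 1 says the depot "was approved for the treatment of schizophrenia in the US in February 2013" and lists it among the US marketed indications. Protocol 3.1 also foresees countries with limited, delayed or no commercialisation.

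**Exposure and duration.** SAP 5.2 (CT-1.3) tabulates duration by month. SAP 5.5.7.2 (CT-7.1 to CT-7.3) summarises the percentage of subjects injected, dose level and trial day, injection by injection. Total patient-years are not planned. None of these tables is stated to be split by US v non-US, and none is linked to the adverse event counts.

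**The concern.** The share of subjects with at least one event rises with time observed, even when the risk per year is constant. Here the time observed varies widely between subjects, and part of the variation is set by where they live. This affects two uses of the tables.

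- **Against Study 248.** The secondary objective is long-term safety data in addition to the 52 weeks of that study. A percentage accumulated over mixed follow-up, some of it several years long, has no defined period, so it cannot be set beside a 52-week percentage. An event count without time has the same defect.
- **US v non-US.** If the US stopped earlier because the product was launched there earlier, CT-17.1 would be expected to show lower US incidence at an identical yearly risk. Nothing in the table would reveal the cause.

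The analysis is descriptive and no hypothesis is tested, so what is at stake is interpretation of the primary outcome measures, not an error rate.

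**Working it through.** The plan has no figure of its own to reproduce: there is no sample size calculation and no adverse event rate. The check covers the follow-up range and its effect on crude incidence.

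**Inputs from the documents**
- Last scheduled visit Month 104, study month 28 days (Protocol 3.6.1.2, Table 3.6-1).
- Study end 31 Dec 2018 (Protocol 3.1); US approval February 2013; EU application December 2012 (Protocol section 1).
- The SAP writes no formula for adverse event incidence. Its one explicit incidence formula (5.5.4, for ECG abnormalities) is subjects with an abnormality over subjects exposed and evaluated, with no time term. The title of CT-8.2.4.3, which uses a cut-off of 5% of subjects, reads the same way.

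**Assumptions (not in the documents).** Constant event hazard L per year, constant hazard D per year of leaving for other reasons, and a fixed stop at T years.

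**Follow-up range**
- Ceiling: 104 x 28 = 2912 days; 2912 / 365.25 = 7.97 years.
- 28 Feb 2013 to 31 Dec 2018 = 2132 days = 5.84 years. This is the most by which a country without a launch could continue beyond US approval.

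**Crude incidence**

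Crude incidence = L/(L+D) x (1 - exp(-(L+D)T)). With D = 0 this is 1 - exp(-LT).

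For L = 0.10 and D = 0:

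| Follow-up | Crude incidence |
|---|---|
| 52 weeks | 9.5% |
| 2 years | 18.1% |
| 3 years | 25.9% |
| 5 years | 39.3% |
| 7.97 years | 54.9% |

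Same hazard in both regions, L = 0.10:

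| Stops (years) | D | Shorter | Longer | Ratio |
|---|---|---|---|---|
| 1 v 3 | 0 | 9.5% | 25.9% | 2.7 |
| 1 v 3 | 0.2 | 8.6% | 19.8% | 2.3 |
| 1 v 3 | 0.4 | 7.9% | 15.5% | 2.0 |
| 2 v 3 | 0 | 18.1% | 25.9% | 1.4 |

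For a common event (L = 1.0, D = 0, stops at 2 v 5 years) the figures are 86.5% and 99.3%, a ratio of 1.15.

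The wider grid took L = 0.05, 0.1, 0.2, 0.4 and 1.0; D = 0, 0.2 and 0.4; and stops at 2/3, 1/3, 2/5, 1/5 and 0.5/2 years. The ratio ran from 1.05 (L = 1.0, D = 0.4, 2 v 3 years) to 4.54 (L = 0.05, D = 0, 1 v 5 years). The true ratio is 1 throughout.

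**Person-time alternative**

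Mean time at risk to first event = (1 - exp(-(L+D)T))/(L+D). Dividing crude incidence by it gives L whatever T and D are. For L = 0.10, D = 0.2, the 1-year stop gives 0.0864 / 0.864 = 0.10 and the 3-year stop 0.1978 / 1.978 = 0.10.

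**The case against.** **Regional follow-up is unknown.** The stopping trigger is launch, not approval, and the documents give no launch dates, entry dates or follow-up by region. With an EU application filed in December 2012, many non-US subjects may have stopped soon after US subjects. This stands as a limit on size. The direction is still supported: the protocol describes the depot as marketed in the US, while Amendment 4 of July 2015 keeps treatment going elsewhere until as late as 31 Dec 2018.

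**The large figures are corners of the grid.** This also stands. The 4.54 needs no other exits and stops at 1 v 5 years; the largest ratio is 3.3 at D = 0.2 and 2.9 at D = 0.4. For stops at 2 v 3 years the range is 1.05 to 1.46. Counting 2912 days back from 31 Dec 2018, only subjects who entered by about 10 January 2011 could reach 7.97 years, and the SAP's last visit window opens at day 1504 (4.1 years).

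**Exposure tables already exist.** Shown injection by injection, they approximate a retention curve, and a reader could estimate overall exposure and divide event counts by it. That would be rough, would not give first events per time at risk, and is not available by region in the planned tables.

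**No comparison is planned, and rates would not make the studies like for like.** Only Study 248 completers enter, and a single rate assumes a roughly constant hazard. Both are true. Rates would still remove one avoidable distortion, and a by-year table lets the reader check the hazard.

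**Conclusion.** The concern holds. The planned adverse event summaries are crude incidences and raw counts; follow-up varies from weeks to a scheduled maximum of 7.97 years and is tied partly to country. Overall incidence cannot be read against 52 weeks, and the US v non-US table is likely to mix follow-up with risk.

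The missing denominator is a fact of the plan. The size of the regional distortion is illustrative: under constant hazards and assumed stop times, a true ratio of 1 appears as anything from 1.05 to 4.5. It is smallest when the regional gap is short or the event common, and it vanishes if follow-up is equal. The change should be made, but as an improvement to a descriptive safety analysis; no formal inference is affected.

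**What to change.** In SAP 5.5.1:

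1. Report total patient-years and the distribution of follow-up overall, by region (US, non-US) and by enrolment source.
2. For TEAEs, serious TEAEs, TEAEs leading to discontinuation and adverse events of special interest, add subjects with a first event per 100 patient-years at risk and events per 100 patient-years. Use these as the comparative measure in CT-17.1 and in the enrolment-source columns.
3. Add incidence by year on treatment with numbers at risk.
4. Define time at risk. The TEAE definition has no end date and adverse events are collected up to the 30-day call, so the SAP should say when risk time ends and that it is censored at the first event for first-event rates.
5. Keep the crude percentages alongside.

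The cost is SAP text, an at-risk convention, derivations from injection and adverse event dates already collected, and some extra tables. It needs no new data and no change to trial conduct.

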### **5.5.2 Clinical Laboratory Tests**

Clinical laboratory tests include serum chemistry analysis, hematology analysis, urinalyses and other lab analysis. The potentially clinically relevant laboratory test abnormalities will be listed by subject and by test for the safety sample, respectively. Criteria for the potentially clinically relevant laboratory test abnormalities per protocol are provided in [Appendix 1](#). Per Hy's law, the subjects with AST or ALT  $\geq 3$  x upper limit of normal value and total bilirubin  $\geq 2$  x upper limit of normal values will be listed as the potential Hy's law cases. The incidences of potentially clinically relevant laboratory tests abnormalities based on the observation from the scheduled and the unscheduled post-baseline visits will be tabulated. In addition, incidence of potentially clinically relevant laboratory tests in potassium ( $\leq 3.0$  mEq/L or  $\geq 5.5$  mEq/L) and neutrophils ( $\leq 1500/\text{mm}^3$ ) per FDA recommendation will be provided. Summary statistics (frequency, mean, standard deviation, minimum, and maximum) for the clinical laboratory measurements at all scheduled visits, and changes from baseline at scheduled visit and last visits will be presented for the safety sample.

If laboratory tests assessments are repeated for the same visit, the last repeated values are used for summary tables. This is accomplished by sorting patient data by visit date and visit time (if applicable) within the same visit identification. If the lab data are recorded as ranges (i.e., including below or above limit of quantification), these data are not

included in the calculations for changes from baseline but included in the calculations for incidence.

The incidence of prolactin level above the upper limit of normal range (potentially clinically relevant change) will be tabulated by gender and the designated visits for the safety sample. The change from baseline in prolactin levels will be presented by gender at scheduled visit and last visit for the safety sample.

Additionally, incidence of treatment-emergent clinically relevant changes in fasting lipid parameters and glucose (as defined in [Table 5.5.2-1](#)) will be summarized for the safety sample.

Table 5.5.2-1 Treatment-emergent Clinically Relevant Changes in Lipids Parameters and Glucose		
Parameters	Baseline	Post-baseline
Total Cholesterol(mg/dL), fasting		
	Normal <200	High >=240
	Borderline 200~<240	High >=240
	Normal/Borderline <240	High >=240
	Normal <200	Borderline/High >=200
	Any Value	Increased >=40
LDL Cholesterol(mg/dL), fasting		
	Normal <100	High >=160
	Borderline 100~<160	High >=160
	Normal/Borderline <160	High >=160
	Normal <100	Borderline/High >=100
	Any Value	Increased >=30
HDL Cholesterol(mg/dL), fasting		
	Normal >=40	Low<40
	Any Value	Decreased >=20
Triglycerides(mg/dL), fasting		
	Normal <150	High >=200
	Normal <150	Very High >=500
	Borderline 150~<200	High >=200
	Borderline 150~<200	Very High >=500
	Normal/Borderline <200	High >=200
	Normal/Borderline <200	Very High >=500
	Normal <150	Borderline/High/Very High >=150
	Normal/Borderline /High >=200	Very High >=500
	Any Value	Increased >=40
Glucose(mg/dL), fasting		
	Normal <100	High >=126

Parameters	Baseline	Post-baseline
	Impaired Fasting Glucose 100~<126	High $\geq 126$
	Normal/ Impaired Fasting Glucose <126	High $\geq 126$
	Any Value	Increased $\geq 10$

Note: The National Cholesterol Education Program (NCEP) Adult Treatment Program Classifications of lipids (refer to fasting lipid measurements) are used for lipid parameters and the American Diabetes Association Criteria are used for glucose.

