### **2.2 Secondary Objective**

The secondary objective of this trial is to collect long-term safety data on aripiprazole IM Depot in addition to what was collected in trial 248 (52-weeks).

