## **4 Sample Size and Power Justification**

In this open-label, single arm rollover trial, no formal sample computations were employed. The anticipated number of subjects from Trial 248 that is predicted to enroll in this trial is approximately 500 to 800.

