In summarizing the incidence of abnormalities, a subject must have had an evaluation that meets abnormality criteria by the end of trial. Incidence rate will be calculated as the number of subjects having at least one abnormality within the trial divided by the number of subjects who are both exposed to trial medication and have an on-treatment evaluation. In addition, incidences of categorical change in ECG - QTc will be provided for change from baseline >30 millisecond, change from baseline >60 millisecond, new onset >450 millisecond, new onset >480 millisecond and new onset >500 millisecond for the safety sample. Change from baseline in ECG parameters will be calculated at scheduled visit and last visit for the safety sample.

If ECG assessments are repeated for the same visit, the last repeat values are used for production of mean change from baseline. This is accomplished by sorting subject data by visit date and visit time (if applicable) within the same visit identification.

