**Appendix 3 Clinical Relevance Criteria for ECG Abnormalities**

Variable	Criteria/Change relative to Baseline
Rate	
Tachycardia	≥ 120 bpm and increase of ≥ 15 bpm
Bradycardia	≤ 50 bpm and decrease of ≥ 15 bpm
Rhythm	
Sinus tachycardia	≥ 120 bpm and increase of ≥ 15 bpm
Sinus bradycardia	≤ 50 bpm and decrease of ≥ 15 bpm
Supraventricular premature beat	Not present → present
Ventricular premature beat	Not present → present
Supraventricular tachycardia	Not present → present
Ventricular tachycardia	Not present → present
Atrial fibrillation	Not present → present
Atrial flutter	Not present → present
Conduction	
1  A-V Block	PR ≥ 0.20 sec and increase of ≥ 0.05 sec
2  A-V Block	Not present → present
3  A-V Block	Not present → present
Left bundle-branch block	Not present → present
Right bundle-branch block	Not present → present
Pre-excitation syndrome	Not present → present
Other intraventricular conduction block	QRS ≥ 0.12 sec and increase of ≥ 0.02 sec
Infarction	
Acute or Subacute	Not present → present
Old	Not present - present at ≥ 12 weeks post entry into the trial
ST/T Morphology	
Myocardial Ischemia	Not present → present
Symmetrical T-wave inversion	Not present → present
QTc	≥ 450 msec and ≥ 10% increase from baseline

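### For about 15 absolute-threshold laboratory tests, including prolactin, the SAP's incidence tables mix abnormalities already present at the on-treatment baseline with new ones

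*SAP*

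**What the plan says.** SAP 5.5.2 applies the Appendix 1 criteria to post-baseline data: "The incidences of potentially clinically relevant laboratory tests abnormalities based on the observation from the scheduled and the unscheduled post-baseline visits" are to be tabulated. It adds absolute criteria for potassium (≤3.0 or ≥5.5 mEq/L) and neutrophils (≤1500/mm³). On prolactin it says: "The incidence of prolactin level above the upper limit of normal range (potentially clinically relevant change) will be tabulated by gender". No baseline condition is stated for numerator or denominator in any of these.

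The only explicit incidence formula is in the ECG section, SAP 5.5.4: "Incidence rate will be calculated as the number of subjects having at least one abnormality within the trial divided by the number of subjects" who were exposed and have an on-treatment evaluation. It does not restrict the denominator to subjects free of the abnormality at baseline either.

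SAP 5.1.2 takes baseline from the last Trial 248 visit with data, and Protocol 7.1 notes that all subjects have already been exposed to the drug. The secondary objective (SAP 2.2) is "to collect long-term safety data on aripiprazole IM Depot in addition to what was collected in trial 248".

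**The concern.** A subject whose prolactin was above the limit at the end of Trial 248 and stays there meets the counting rule at the first post-baseline sample, exactly as a subject who crosses the limit for the first time does. The tabulated percentage cannot be separated into the two.

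That matters more here than in a study with a drug-free baseline. The baseline is on treatment, and the stated purpose is to add to what Trial 248 already showed. The added information lies in new or worsened abnormalities.

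The rule is also out of line with most of the SAP, which ties safety findings to baseline. The description of prolactin above the limit as a change shows the tension within a single sentence.

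**Working it through.** **1. How the SAP treats baseline elsewhere**

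- Adverse events (5.5.1): an event must start after dosing or, if continuing from baseline, worsen or meet another listed condition.
- Vital signs (Appendix 2): a cut-off and a change from baseline are both needed. Orthostatic hypotension is the exception; Protocol Appendix 3 says that baseline is disregarded for it.
- ECG (Appendix 3): a change, or absent before and present after. For QTc the rule is "≥ 450 msec and ≥ 10% increase from baseline".
- C-SSRS (5.5.6.3): emergence requires absence at baseline.
- Fasting lipids and glucose (Table 5.5.2-1): shifts defined by baseline category, plus increases or decreases from any baseline value.
- Appendix 1 laboratory criteria and prolactin: mostly absolute cut-offs, with no baseline condition.

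**2. How many tests are affected**

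Appendix 1 lists 10 chemistry, 6 hematology, 3 urinalysis and 9 additional tests: 10 + 6 + 3 + 9 = 28.

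- Change built in: hematocrit, and urine protein, glucose and casts (reading the urinalysis increase as relative to baseline). 28 − 4 = 24 absolute criteria.
- Separate baseline-conditioned table: glucose, total cholesterol, LDL, HDL and triglycerides, all fasting. 24 − 5 = 19. Their Appendix 1 counts remain unconditioned.
- Excluded at baseline at essentially the same threshold (Protocol Table 3.4.3-1, item 9): AST, ALT, creatinine and low platelets. 19 − 4 = 15.

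The 15 are alkaline phosphatase, LDH, BUN, uric acid, bilirubin, CPK, prolactin, hemoglobin, white cells, eosinophils, neutrophil percentage, chloride, potassium, sodium and calcium. Chloride is not in the protocol's laboratory table (3.6.3.2-1), so the working number may be 14. The added potassium and neutrophil criteria are open too.

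Hemoglobin and neutrophils stay open despite their exclusions because the exclusion limits are more extreme than the reporting limits. Hemoglobin is excluded at ≤9 g/dL but reported at ≤11.5 (men) or ≤9.5 (women). Neutrophils are excluded at ≤1000/mm³ but reported at ≤1500/mm³.

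**3. Size, as illustration only**

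There is no planned figure to reproduce: "no formal sample computations were employed", and no laboratory rate is given. Let p be the proportion meeting the criterion at baseline, s the proportion of those who meet it again later, and n the new-onset proportion among the rest. Everyone is assumed to have baseline and post-baseline values.

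- Tabulated rate = p·s + (1 − p)·n, over all subjects.
- Emergent rate = n, over subjects not meeting the criterion at baseline.
- Carried-over share of counted cases = p·s / [p·s + (1 − p)·n].

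The value p = 3.4% comes from Protocol 1.3: prolactin above the upper limit in one 52-week oral-aripiprazole study. It stands in for an unknown prevalence. The values s = 80% and n = 5%, and all larger p, are assumptions.

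| p | p·s | (1 − p)·n | Tabulated | Emergent | Carried-over share |
|---|---|---|---|---|---|
| 3.4% | 2.72% | 4.83% | 7.55% | 5.0% | 36% |
| 10% | 8.0% | 4.5% | 12.5% | 5.0% | 64% |
| 20% | 16.0% | 4.0% | 20.0% | 5.0% | 80% |
| 30% | 24.0% | 3.5% | 27.5% | 5.0% | 87% |

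With 500 subjects, the lower end of the SAP's 500 to 800, the first row is about 38/500 tabulated against 24/483 emergent. The percentages do not depend on the number enrolled.

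Across p from 3.4% to 30%, s from 50% to 80% and n from 2% to 10%, the carried-over share runs from 15% (0.017/0.1136) to 94% (0.24/0.254).

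**The case against.** Counting any on-treatment abnormality is a conventional and conservative safety summary. The SAP keeps the two ideas apart by name: the baseline-conditioned tables (CT-13.1.2, CT-13.1.3) are titled as shifts, while CT-13.1.1 is titled as incidence of values of potential relevance. So a reader might infer that carried-over abnormalities are being presented as new findings, but the text does not say so. It is silent on baseline status, and only the label attached to prolactin leans that way. A reader might also infer that Trial 248 findings are counted twice; neither document describes pooling the two trials. Both points stand.

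Other outputs help in part. Change from baseline is summarized for laboratory tests, and for prolactin by sex; abnormal values are listed by subject and by test. Under Protocol 5.1, a result the investigator judges an abnormal change from that subject's baseline becomes an adverse event. But mean changes do not show how many subjects crossed a limit, and values recorded as ranges are left out of them while entering the incidence. Listings give no rate, and the adverse-event route depends on judgement. If the by-visit prolactin table includes a baseline column, carry-over would show in aggregate; the SAP does not say that it will.

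Baseline exclusions do remove most carry-over for AST, ALT, creatinine and low platelets. Subjects may enroll before results arrive, but those with clinically significant results are to be withdrawn.

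The strongest objection is to the obvious remedy. Counting only subjects below the threshold at baseline would drop those who were abnormal and then worsened, and could hide a continuing drug effect. That stands and shapes the fix.

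**Conclusion.** The point holds in limited form. For about 15 absolute-threshold tests, plus the added potassium and neutrophil criteria, the laboratory incidence tables as written cannot separate persisting from new abnormalities, and no other planned table does so for them. It is not a defect of the whole laboratory analysis: hematocrit and urinalysis are unaffected, four tests are largely protected, and fasting lipids and glucose have their own shift table.

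The size is unknown. A reader might infer a very large distortion by supposing that 30% or 50% of subjects are abnormal at baseline, but nothing in the documents supports such figures. With the one figure available, 3.4%, and the assumed 80% persistence and 5% onset, the gap is 7.55% against 5.0%. That figure comes from the oral drug and is not a prevalence among Trial 248 completers.

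The study is single-arm and descriptive, so no test, power or sample-size statement is affected. This is a cheap improvement in how well the tables serve the secondary objective.

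**What to change.** In CT-13.1.1, CT-13.1.4 and CT-13.2.5.1:

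- Keep the present count, labelled as any post-baseline value meeting the criterion, regardless of baseline.
- Add treatment-emergent incidence. Numerator: subjects who meet the criterion post-baseline and did not at baseline. Denominator: subjects with a baseline value not meeting the criterion and at least one post-baseline value.
- Add a row for subjects who met the criterion at baseline, showing how many persist and, among those, how many worsen. State the rule for worsening beforehand.
- Show subjects with no baseline value separately, so that the parts add up to the any-post-baseline count.

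For prolactin, either drop the description of a value above the limit as a change or attach it only to the treatment-emergent row.

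No new data are needed. The cost is extra rows, a worsening rule, and smaller denominators for the treatment-emergent rate: 483 instead of 500 at 3.4% baseline prevalence, 400 instead of 500 at 20%.
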